### 9.2.2.2 IT Immunotherapy RECIST (itRECIST)

itRECIST, a response assessment tailored to IT immunotherapy, is aligned with RECIST 1.1 overall response assessment [Goldmacher, G. V., et al 2020] and is further described in Appendix 8, Section 12.8.

### itRECIST:

- provides a guidance on baseline categorization of target and nontarget lesions (Figure 3).
- provides guidance on recategorization of lesions during therapy (Figure 4).
- allows for separate response assessment in injected and noninjected lesions (Figure 5).

**Protocol/Amendment No.:** 001-08

• for injected lesions, provides an iterative response assessment process that adapts to changes in lesion selection for IT immunotherapy (an example is provided in Figure 6).

• provides guidelines on prioritization of lesion injection during the course of IT immunotherapy (see Appendix 12.7).

itRECIST supports standardized collection of data from IT immunotherapy clinical trials to facilitate exploratory response analysis.

# 9.2.2.3 IWG Revised Response Criteria for Malignant Lymphomas

Response to treatment for lymphomas will be assessed every 12 weeks ( $\pm$  7 days) from the first dose of treatment.

Response to therapy will be assessed by CT, with or without PET, and bone marrow biopsy, and clinical information including physical examination and symptoms (fever, night sweats, weight loss), using the IWG revised response criteria for malignant lymphomas [Cheson, B. D., et al 2007]. Information collected for this assessment includes:

- 1. At a minimum, thoracic, abdominal, and pelvic CT scans will be performed even if those areas were not initially involved because of the unpredictable pattern of recurrence in malignant lymphoma. Neck CT should be performed at screening, at follow-up visits if there is nodal involvement in the neck at screening. FDG-PET scans may be obtained to supplement the anatomic imaging, and should always be collected at screening, 12 weeks, 24 weeks, and when CR is suspected.
- 2. Unilateral bone marrow biopsy and aspirates will be performed at Screening, if not previously performed within 8 weeks prior to Screening with negative results. The bone marrow biopsy will be performed to confirm a CR if the participant was initially positive or if it is clinically indicated by new abnormalities in the peripheral blood counts or blood smear.

Response of lesions will be recorded on the eCRF based on the definitions in Table 15 as appropriate. Suspected relapse or disease progression must be confirmed by physical examination, laboratory assessments, repeat bone marrow biopsy [Cheson, B. D., et al 2007], and CT scan. Participants with suspected relapse or disease progression should continue to follow study procedures until they need another therapy. If a participant requires another therapy, date of treatment and type of treatment will be recorded, and they will then be removed from the trial.

Tumor progression is defined as  $\geq$ 50% increase from nadir in the SPD of target lesions, or by growth of a single nodal target lesion, or by growth of nontarget lesions, or the appearance of new lesions, as defined in the IWG revised response criteria for malignant lymphoma [Cheson, B. D., et al 2007]. For purposes of this protocol, biopsied tumors should not be used for assessment by revised IWG criteria, except in cases with only target lesions available, after consultation with the Sponsor.

**Protocol/Amendment No.:** 001-08

Table 15 Response Criteria for Malignant Lymphoma

Response Category	Physical Examination	Nodal Masses	Spleen, Liver	Bone Marrow
Complete Response	Disappearance of all evidence of disease	(a) FDG-avid or PET positive prior to therapy; mass of any size permitted if PET negative (b) Variably FDG-avid or PET negative; regression to normal size on CT	Not palpable, nodules disappeared	Infiltrate cleared on repeat biopsy; if indeterminate by morphology, immunohistochemistry should be negative
Partial Response	No progression of palpable disease and no new sites	≥50% decrease in SPD of up to 6 largest dominant masses; no increase in size of other nodes (a) FDG-avid or PET positive prior to therapy; one or more PET positive at previously involved site (b) Variably FDG-avid or PET negative; regression on CT	≥50% decrease in SPD of nodules (for single nodule in greatest transverse diameter); no increase in size of liver or spleen	Irrelevant if positive prior to therapy; cell type should be specified
Stable Disease	Failure to attain CR/PR or PD	(a) FDG-avid or PET positive prior to therapy; PET positive at prior sites of disease and no new sites on CT or PET (b) Variably FDG-avid or PET negative; no change in size of previous lesions on CT		
Relapse/ Progression	Any new lesion or increase by ≥ 50% of previously involved sites from nadir	Appearance of a new lesion(s) 1.5 cm in any axis, ≥50% increase in SPD of more than one node, or ≥50% increase in longest diameter of a previously identified node >1 cm in short axis  Lesions PET positive if FDG-avid lymphoma or PET positive prior to therapy	≥50% increase from nadir in the SPD of any previous lesions	New or recurrent involvement

Abbreviations: CR = complete response; CT = computed tomography; FDG = fluorodeoxyglucose; PD = progressive disease; PET = positron emission tomography; PR = partial response; SPD = Sum of the products of the greatest diameters.

**Protocol/Amendment No.:** 001-08

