# 9.3.1 Time Period and Frequency for Collecting AE, SAE and Other Reportable Safety Event Information

Progression of the cancer under study is not considered an AE unless it results in hospitalization or death.

All AEs, SAEs and other reportable safety events that occur after the consent form is signed, but before treatment allocation/randomization, must be reported by the investigator if the participant is receiving placebo run-in or other run-in treatment, if the event cause the participant to be excluded from the trial, or is the result of a protocol-specified intervention, including, but not limited to, washout or discontinuation of usual therapy, diet, or a procedure.

- All AEs from the time of treatment allocation/randomization through 30 days following cessation of study treatment must be reported by the investigator.
- All AEs meeting serious criteria, from the time of treatment allocation/randomization through 120 days following cessation of study treatment, or 30 days following cessation of study treatment if the participant initiates new anticancer therapy, whichever is earlier must be reported by the investigator.
- All pregnancies and exposure during breastfeeding, from the time of treatment allocation/randomization through 120 days following cessation of study treatment, or 30 days following cessation of study treatment if the participant initiates new anticancer therapy must be reported by the investigator.
- Additionally, any SAE brought to the attention of an investigator at any time outside of
  the time period specified above must be reported immediately to the Sponsor if the
  event is considered to be drug-related.

Investigators are not obligated to actively seek AE or SAE or other reportable safety events in former study participants. However, if the investigator learns of any SAE, including a death, at any time after a participant has been discharged from the study, and he/she

Protocol/Amendment No.: 001-08

considers the event to be reasonably related to the study treatment or study participation, the investigator must promptly notify the sponsor.

All initial and follow-up AEs, SAEs and other reportable safety events will be recorded and reported to the sponsor or designee within the timeframes as indicated Table 22.

Table 22 Reporting Time Periods and Timeframes for Adverse Events and Other Reportable Safety Events

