# 9.10.3.1 30-Day Safety Follow-up Visit

The mandatory 30-day Safety Follow-up Visit should be conducted approximately 30 days (+7 days) after the last dose of trial treatment or before the initiation of a new anticancer treatment, whichever comes first. All AEs that occur prior to the 30-day Safety Follow-up Visit should be recorded. Participants with an AE of Grade >1 will be followed up until resolution of the AE to Grade 0-1 or until the beginning of a new antineoplastic therapy, whichever occurs first.

After the EOT, each participant will be followed up for at least 30 days for AE monitoring and 120 days for SAEs, ECIs, and spontaneously reported pregnancy. SAEs, ECI, and spontaneously reported pregnancy will be reported for 30 days after the EOT if the participant initiates new anticancer therapy. Progression of the cancer under study is not considered an AE.

Participants who are eligible for crossover to combination therapy with IT MK-2118 and pembrolizumab may have up to 2 safety follow-up visits, 1 after monotherapy (Arm 1) and 1 after combination therapy (Arm 2).

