## 9.10.3.2 Survival Follow-up

All participants, with the exception of those who withdraw consent or are lost to follow-up, will be followed up for survival and will be contacted every 12 weeks ( $\pm 14$  days) to monitor survival status. Participants who experience confirmed disease progression or start a new anticancer therapy, will move into the Survival Follow-Up Phase and should be contacted approximately every 12 weeks to assess for survival status until death, withdrawal of consent, or the end of the study, whichever occurs first.

To ensure current and complete survival data is available at the time of database locks, updated survival status may be requested during the course of the study by the Sponsor. For

27-Sep-2022 Confidential

08C0RV

**Protocol/Amendment No.:** 001-08

example, updated survival status may be requested prior to, but not limited to, an eDMC safety review, interim and/or final analysis. Upon Sponsor notification, all participants who do not/will not have a scheduled study visit or study contact during the Sponsor-defined time period will be contacted for their survival status (excluding participants that have a previously recorded death event in the collection tool).

Every effort should be made to collect information regarding disease status until the start of new antineoplastic therapy, disease progression, death, or the end of the study.

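### Section 9.2.2.3 takes lymphoma participants out of the trial when they need another therapy, while Sections 8.1 and 9.10.3.2 keep them in follow-up; read literally, it would censor exploratory OS at that point

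*Combined protocol and SAP*

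**What the plan says.** Section 9.2.2.3 gives the response rules for lymphoma under the IWG criteria. On suspected relapse or progression it says: "Participants with suspected relapse or disease progression should continue to follow study procedures until they need another therapy". If another therapy is then required, "date of treatment and type of treatment will be recorded, and they will then be removed from the trial".

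The general sections say something different.

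- **Section 9.10.3.2** opens survival follow-up to "All participants, with the exception of those who withdraw consent or are lost to follow-up", and adds: "Participants who experience confirmed disease progression or start a new anticancer therapy, will move into the Survival Follow-Up Phase". Contact is about every 12 weeks until death, withdrawal of consent or the end of the study.
- **Section 8.1** separates stopping treatment from leaving the study. It lists progression among the reasons for stopping treatment while monitoring in the study continues.
- **Section 8.2** names withdrawal of consent as the ground on which a participant must leave the study.
- **Section 9.3.1** sets the AE window: "All AEs from the time of treatment allocation/randomization through 30 days following cessation of study treatment must be reported by the investigator". For serious AEs (SAEs) the window is 120 days, or "30 days following cessation of study treatment if the participant initiates new anticancer therapy, whichever is earlier".
- **Section 9.10.3.1** repeats the shortened window: "SAEs, ECI, and spontaneously reported pregnancy will be reported for 30 days after the EOT if the participant initiates new anticancer therapy". It also brings the 30-day safety visit forward if new anticancer treatment would start before it, and asks for at least 30 days of AE monitoring after end of treatment.
- **Section 10.4.1** defines OS as exploratory and censors survivors at their last assessment or contact.

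**The concern.** The lymphoma section and the general follow-up sections give opposite instructions for the same participant at the same moment. Section 5.4.1.3 refers to 9.2.2.3 for detail and makes the lymphoma response criteria the basis for protocol guidance on participant status. A site handling a lymphoma case could therefore reasonably treat 9.2.2.3 as the specific rule that overrides the general one.

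If it did, survival contacts would stop when the next therapy begins. Under the Section 10.4.1 rule the OS time is then censored at about that date. People usually need a next therapy because the disease is progressing, so those censored would tend to carry a higher risk of death than those still followed. Kaplan-Meier estimation assumes that the two groups have the same risk.

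The second thing at stake is the safety window. AEs are a primary endpoint, and ending participation at a new therapy could close AE and SAE collection before day 30.

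**Working it through.** The plan gives no figure for this point, so there is nothing to reproduce. Section 10.9 sizes the trial on dose-finding cohorts (3 × 35 + 55 = 160), and OS does not enter that count.

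**Step 1: the texts side by side, for a lymphoma participant who starts another therapy**

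| Question | Section 9.2.2.3 | General sections |
|---|---|---|
| Still in the study? | No | Yes (8.1, 9.10.3.2) |
| Survival contacts? | None provided for | About every 12 weeks (9.10.3.2 and the post-treatment schedule in 2.5) |
| AE and SAE collection? | None provided for | Through 30 days after cessation (9.3.1) |

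The exemptions in 9.10.3.2 are withdrawn consent and loss to follow-up. Lymphoma is not among them. Section 7.7 prohibits no therapies during follow-up visits, which fits a plan that expects people on new therapy to stay in follow-up. Cutaneous T-cell lymphoma is assessed under 9.2.2.4, which has no removal sentence, so the affected group is lymphoma assessed by IWG criteria.

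**Step 2: how far OS could move**

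The inputs are not in the documents, so all of the following are assumptions:

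- exponential times;
- median time to progression 3 months;
- median time to death without progression 24 months;
- median survival after progression 4 or 8 months;
- new therapy 1 month after progression in 50% or 80% of those who progress, unrelated to their later prognosis;
- follow-up to 24 months;
- lymphoma share of the analysed group from 5% to 100%.

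Kaplan-Meier estimates from 400,000 simulated participants per scenario compare full follow-up with censoring of lymphoma participants at new therapy.

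| Lymphoma share | New therapy | Post-progression median | Median OS, full → censored (months) | 12-month OS, full → censored |
|---|---|---|---|---|
| 100% | 50% | 4 months | 7.3 → 8.2 | 26.0% → 31.3% |
| 100% | 80% | 4 months | 7.3 → 9.5 | 25.8% → 38.4% |
| 100% | 50% | 8 months | 10.9 → 11.7 | 45.7% → 48.8% |
| 100% | 80% | 8 months | 10.9 → 12.9 | 45.7% → 53.3% |
| 30% | 80% | 4 months | 7.4 → 7.7 | 26.0% → 28.0% |
| 5% | 80% | 8 months | 10.9 → 10.9 | 45.7% → 45.8% |

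In a lymphoma-only analysis the median rises by 0.8 to 2.2 months (11.7 − 10.9 and 9.5 − 7.3). Across all pooled scenarios with a 5% to 30% share it rises by about 0 to 0.3 months, and 12-month OS by about 0.1 to 2 points.

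**Step 3: the most that could be lost from the AE window**

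Let t be the days from last dose to new therapy. With removal at new therapy, days lost = max(0, 30 − t).

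- t = 7: 23 days
- t = 14: 16 days
- t = 21: 9 days
- t = 28: 2 days
- t ≥ 30: 0 days

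The last line holds for SAEs too, because 9.3.1 already shortens their window to 30 days once new therapy starts. These figures are ceilings, since 9.10.3.1 moves the safety visit forward in exactly these cases.

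**The case against.** The best defence is that one clause in a response-criteria subsection does not override the sections that govern follow-up. Section 9 makes adherence to the schedule of activities essential, and that schedule has survival follow-up for Arms 1 to 4 without exception. The clause may have been meant as removal from study treatment, and a site that follows 8.1 and 9.10.3.2 loses nothing. The sponsor may also request survival status at any time during the study. All of this stands, and it makes the harm conditional. It does not remove the contradiction: 9.2.2.3 ends study procedures at the need for another therapy and then refers to the trial, not to treatment.

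A reader might infer more than the documents support.

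- **That AEs are lost as a matter of course.** They are not. Section 9.10.3.1 brings the safety visit forward before new treatment for every participant, whatever the tumour type. Follow-up of unresolved events above Grade 1 already runs only "until resolution of the AE to Grade 0-1 or until the beginning of a new antineoplastic therapy". Drug-related SAEs that come to the investigator's attention stay reportable at any time under 9.3.1. The ordinary AE rule in 9.3.1 does not mention new therapy at all, so the general sections are themselves unclear on what happens between an early visit and day 30.
- **That the primary safety results or dose-finding are compromised.** DLTs are counted over 21 days, or 35 in Arm 4, from the first dose. No route from this clause to DLT evaluation is shown.
- **That participants are removed at progression.** The trigger is the next therapy. Until then they continue study procedures.
- **That OS is in fact informatively censored.** This depends on which section sites follow, and the documents do not say. OS methods sit in a supplemental SAP that is not part of these documents.

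**Conclusion.** The contradiction is real and unreconciled in the current text. Its main consequence is conditional: if sites follow 9.2.2.3 literally, OS for IWG-assessed lymphoma participants is censored at about the start of the next therapy. That censoring is likely informative and would tend to push OS upward.

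The size cannot be fixed from the documents, because lymphoma enrolment and the rate and timing of next therapy are not given. The simulated shifts are illustrations, and their direction rests on next therapy being unrelated to prognosis after progression. If those who receive it are the fitter patients, the bias would be smaller and could reverse.

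The AE effect is secondary and narrow. It is limited to new therapy less than 30 days after the last dose and partly covered by the early safety visit. OS is exploratory, and neither DLT evaluation nor sample size is shown to be affected. The point is worth correcting because the loss is avoidable and the correction is small.

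**What to change.** Reconcile the passages by replacing the last clause of that sentence in Section 9.2.2.3. Suggested wording: the date and type of the new treatment will be recorded; the participant remains in the study and enters safety follow-up per Sections 9.3.1 and 9.10.3.1 and survival follow-up per Section 9.10.3.2. Leave the treatment rules as they are.

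In the same amendment, the sponsor could state in 9.10.3.1 whether ordinary AE collection continues to day 30 when the safety visit has been brought forward.

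If any lymphoma participant has already left at the next therapy, the existing provision for survival-status requests can be used to recover the information where consent allows. Any OS time still censored for this reason should be identified in the study report.

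The cost is one sentence, plus an optional clarification. No new visits are needed, because the safety visit and the 12-weekly contacts are already planned.

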# 9.2.2.4 Response Assessment for Cutaneous T-cell Lymphoma

The mSWAT (Table 16) will be used to evaluate the extent of disease in the CTCL participants prior to treatment at each cycle per the SoA. Imaging (CT scans and medical photography) will be performed at screening/baseline for all CTCL participants. In those patients with advanced disease at baseline (maximum/current stage greater than or equal to Stage IIB (T3N0M0B0)), repeat imaging studies should be performed at the time of PR and CR by assessment of the skin, and any time there is a question of new or PD in the lymph nodes or the viscera; and at the end of the study [Olsen, E. A., et al 2011].

Each scheduled response assessment will include evaluations of skin (Table 17), lymph nodes (Table 18), viscera (Table 19), and blood (Table 20); and will determine a global response score (Table 21) for CTCL participants. Medical photography will also be performed at the time of each response assessment (see SoA), or more often as warranted.

Table 16 Modified Severity Weighted Assessment Tool

Body Regions	% BSA in Body Region	Assessment of Involvement in Patient's Skin		
•		Patch a	Plaque b	Tumorc
Head	7			
Neck	2			
Anterior trunk	13			
Arms	8			
Forearms	6			
Hands	5			
Posterior trunk	13			
Buttocks	5			
Thighs	19			
Legs	14			
Feet	7			
Groin	1			
Subtotal of lesion BSA		× 1	× 2	× 4
Weighting factor				
Subtotal lesion BSA ×				
weighting factor				

Abbreviations: BSA = body surface area; mSWAT = modified Severity Weighted Assessment Tool NOTE: mSWAT score equals summation of each column line

08C0RV

<sup>a.Any size lesion without induration of significant elevation above the surrounding uninvolved skin; poikiloderma may be present.

b. Any size lesion that is elevated or indurated, crusting, ulceration, or poikiloderma may be present.

<sup>c. Any solid or nodular lesion  $\geq 1$  cm in diameter with evidence of deep infiltration in the skin and/or vertical growth.

**Protocol/Amendment No.:** 001-08

Table 17 Response in Skin (Cutaneous T-cell Lymphoma)

Response	Definition	
CR	100% clearance of skin lesions	
PR	50%-99% clearance of skin disease from baseline without new tumors $(T_3)$ in patients with $T_1$ , $T_2$ or $T_4$ only skin disease	
SD	<25% increase to <50% clearance in skin disease from baseline without new tumors $(T_3)$ in patients with $T_1$ , $T_2$ , or $T_4$ only skin disease	
PD	Whichever criterion occurs first:	
	≥25% increase in skin disease from baseline	
	OR	
	New tumors (T 3 ) in patients with T 1 , T 2 or T 4 only skin disease OR	
	Loss of response: in those with complete or partial response, increase of skin score of greater than the sum of nadir plus 50% baseline score	
Relapse	Any disease recurrence in those with complete response	

Abbreviations: CR = complete response; PD – progressive disease; PR partial response; SD = stable disease. NOTE. Based on modified Severity Weighted Assessment Tool (mSWAT) score. A biopsy of normal appearing skin is unnecessary to assign a complete response. However, a skin biopsy should be performed of a representative area of the skin if there is any question of residual disease (persistent erythema or pigmentary change) where otherwise a complete response would exist. If histologic features are suspicious or suggestive of mycosis fungoides/Sézary syndrome, the response should be considered a partial response only.

**Protocol/Amendment No.:** 001-08

Table 18 Response in Lymph Nodes (Cutaneous T-cell Lymphoma)

Response	Definition (peripheral and/or central lymph nodes)		
CR	All lymph nodes are now $\leq 1.5$ cm in greatest transverse (long axis) diameter by method used to assess lymph nodes at baseline or biopsy negative for lymphoma; in addition, lymph nodes that were $N_3$ classification and $\leq 1.5$ cm in their long axis and $>1$ cm in their short axis at baseline, must now be $\leq 1$ cm in their short axis or biopsy negative for lymphoma		
PR	Cumulative reduction ≥50% of the SPD of each abnormal lymph node at baseline and no new lymph node >1.5 cm in the diameter of the long axis or >1.0 cm in the diameter of the short axis if the long axis is 1-1.5 cm diameter		
SD	Fails to attain the criteria for CR, PR, and PD		
PD Whichever criterion occurs first:			
	≥50% increase in SPD from baseline of lymph nodes		
	OR		
	Any new node $>1.5$ cm in the long axis or $>1$ cm in the short axis if 1-1.5 cm in the long axis that is proven to be $N_3$ histologically		
	OR		
	Loss of response: >50% increase from nadir in SPD of lymph nodes in those with PR		
Relapse	Any new lymph node >1.5 cm in the long axis in those with CR proven to be N 3 histologically		
Abbreviations:	CR = complete response; PD – progressive disease; PR partial response; SD = stable disease.		

**Protocol/Amendment No.:** 001-08

Table 19 Response in Viscera (Cutaneous T-cell Lymphoma)

Response	Definition	
CR	Liver or spleen or any organ considered involved at baseline should not be enlarged on physical examination and should be considered normal by imaging; no nodules should be present on imaging of liver or spleen; any post treatment mass must be determined by biopsy to be negative for lymphoma	
PR	≥50% regression in any splenic or liver nodules, or in measurable disease (SPD) in any organs abnormal at baseline; no increase in size of liver or spleen and no new sites of involvement	
SD	Fails to attain the criteria for CR, PR, or PD	
PD	Whichever criterion occurs first:  >50% increase in size (SPD) of any organs involved at baseline OR New organ involvement OR Loss of response: >50% increase from nadir in the size (SPD) of any previous organ involvement in those with PR	
Relapse	New organ involvement in those with CR	
Abbreviations:	CR = complete response; PD – progressive disease; PR partial response; SD = stable disease.	

**Protocol/Amendment No.:** 001-08

Table 20 Response in Blood (Cutaneous T-cell Lymphoma)

Responsea	Definition
CR b	$B_0$
PR°	>50% decrease in quantitative measurements of blood tumor burden from baseline in those with high tumor burden at baseline (B 2 )
SD	Fails to attain criteria for CR, PR, or PD
PD	Whichever criterion occurs first: $B_0$ to $B_2$ OR >50% increase from baseline and at least 5,000 neoplastic cells/ $\mu$ L[Cheson, B. D., et al 1996] OR
	Loss of response: in those with PR who were originally B 2 at baseline, >50%increase from nadir and at least 5,000 neoplastic cells/µL
Relapse	Increase of neoplastic blood lymphocytes to $\geq B_1$ in those with CR

Abbreviations: CR = complete response; PD - progressive disease; PR partial response; SD = stable disease. a. As determined by absolute numbers of neoplastic cells/ $\mu L$ .

b. If a bone marrow biopsy was performed at baseline and determined to unequivocally be indicative of lymphomatous involvement, then to confirm a global CR where blood assessment now meets criteria for  $B_0$ , a repeat bone marrow biopsy must show no residual disease or the response should be considered a PR only. c. There is no PR in those with  $B_1$  disease at baseline as the difference within the range of neoplastic cells that define  $B_1$  is not considered significant and should not affect determination of global objective response.

**Protocol/Amendment No.:** 001-08

Table 21 Global Response Score for Cutaneous T-cell Lymphoma

Global Score	Definition	Skin	Nodes, Blood, Viscera	
CR	Complete disappearance of all clinical evidence of disease	CR	All categories have CR/NI	
PR	Regression of measurable disease	CR	All categories do not have a CR/NI and no category has a PD	
		PR	No category has a PD and if any category involved at baseline, at least one has a CR or PR	
SD	Failure to attain CR, PR, or PD representative of all disease	PR	No category has a PD and if any category involved at baseline, no CR or PR in any	
		SD	CR/NI, PR, SD in any category and no category has a PD	
PD	Progressive disease	PD in any category		
Relapse	Recurrence disease in prior CR	Relapse in any category		

Abbreviations: CR, complete response; NI, noninvolved; PR, partial response; PD, progressive disease; SD, stable disease.

